consent document for their information and records. In this consent, the patient will be asked for permission to review their medical charts at Johns Hopkins Hospital for the clinical information of their ED visit. Consented patients will be randomized to one of two groups, the Index Group (Group 1) or the Reference Group (Group 2). The index group or the HIV self-testing kit group will be provided a free FDA-approved HIV self-testing home kit (OraQuick *ADVANCE*® Rapid HIV-1/2 Antibody Test) and the reference group will not receive the HIV self-testing kit. Consented patients in both groups will fill out a short survey regarding their socio-demographic information as well as their experience, attitudes, and perceptions regarding HIV testing. For patients who are in the HIV self-testing kit group, they will be asked if they would like to take a free FDA-approved HIV self-testing home kit home. If they agree, the research staff will make sure the patients will take the kit home when they are discharged. Participants in this group will also receive information regarding how to access the IWTK website to report the completion of HIV self-testing at home. Participants in this group will also be informed of a lottery-based monetary compensation with 1 in 10 chance to win an additional \$50 gift card for reporting the test results to the IWTK website. Participant who wins the \$50 gift card will be notified via text message, followed by a phone call while participant who does not win the gift card will be notified via text message (see section 20 for "Text Message Script for Lottery Incentive). For patients who are in the reference group, a standard pamphlet regarding the importance of HIV testing and HIV testing venues in Baltimore City used by current JHH ED-based HIV testing program will be provided to the patients.

3. Survey information:

- Patients will be consented and enrolled in the study prior to collecting data in the ED.

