- After patient consent and enrollment by the study staff, each study participant will complete a survey questionnaire (see attached Index_Questionnaire.docx in Supplemental Study Documents) at the time of enrollment to indicate their social, demographic, and clinical characteristics. The survey is research (not part of routine care), but would not add to the patient's length of stay since it can be conducted during waiting time in a private setting. This survey will be clearly explained by and completed with the assistance of the study staff.
- All patients will be informed of our intent to contact them for a brief follow-up phone interview at one month and 3 months from the date of enrollment. This is one of the exclusion criteria.
- Following enrollment, a member of the research team will abstract chart data of the ED visits. The abstraction will focus on visit-specific clinical data (e.g. chief complaint, diagnosis, acuity level, and disposition (The full variable list can be found in section 20, Variable List).

4. Patient Follow-up

- Participants will receive a phone or text message reminder from the study team in order to remind that they are enrolled in the study within a week after the enrollment. The study team will make sure that the participant is the one who answers the phone before reminding the participant of this study. The text message will not contain the words of HIV or HIV testing. The participant will also receive text message reminder 1 week before each follow-up time (1 and 3 month time point). The text message will include the reminder of the phone follow-up as well as the \$10 gift card incentive that we would be providing to the participant upon completing the phone follow up (see section 20 for "Text reminder version 0.02).
- Consented patients will be contacted by the study team at one month and 3 months after enrollment. No more than five separate attempts to contact will be made during this time until deemed lost to follow up for the particular follow up time point.
- Follow-up questionnaires will ask the patient about their experience, attitudes, and perceptions regarding HIV testing since their index visit. Please see attached Phone_Script.docx
- A \$10.00 gift card will be mailed to the participant once he/she completes the follow-up survey by phone for each follow up time point.

5. HIV Self-testing at home

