Instructions for performing the home test, with visual aids, will be included with the kit. For participants in the HIV self-testing kit group whose test result by HIV self-testing at home is interpreted as “reactive” or “indeterminate”, he or she can follow the instruction inside the kit to call a hotline to our JHH ED routine rapid HIV screening and LTC program staff that operates 16 hours a day, 7 days a week, OraQuick Consumer Support Center that operates 24 hours a day, or their primary physician for counseling. Patients with a reactive test result can either come to JHH ED or the Johns Hopkins HIV Women’s Program to receive confirmatory blood testing of the screening self-test. All participants with a positive or indeterminate screening result will have blood drawn and sent to the Maryland Department of Health and Mental Hygiene Laboratories Administration Central Laboratory where FREE confirmatory testing will be performed using the HIV-1 Western Blot Assay from BioRad Laboratories. (At MD DHMH Central Laboratory, indeterminate and negative HIV-1 Western Blot specimens are tested using the Multispot HIV-1/HIV-2 Rapid test as a differentiation assay to rule out HIV-2, and using in-house validated HIV-1 real time PCR assay to detect acute cases of HIV-1).

For participants in the HIV self-testing kit group, they will be asked to report their test result on to IWTK website using the access information provided in the HIV self-testing kit.

Aim 3: to determine the feasibility and acceptability of HIV self-testing kit referral among partners or peers of the index participants through drug, sex, or social network

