When the participants (the index participants) in the HIV self-testing kit group in Aim 1 receive the self-testing kit, they will also be provided 5 referral cards to give to their partners and peers in the drug, sex, and social networks for them to request a free HIV self-testing kit from the IWTK website. On the referral card, a unique code number be used after the subject uses provided URL to land in IWTK website and create an IWTK user account. The unique code number will indicate the IWTK user is referred from an ED patient who is an index participant. The index participants would also be informed of a lottery-based monetary compensation to provide 1 in 10 chance to win an additional \$10 gift card for every IWTK user that is referred from an index participant of our study. Participant who wins the \$10 gift card will be notified via text message, followed by a phone call while participant who does not win the gift card will be notified via text message (see section 20 for "Text Message Script for Lottery Incentive). The confidential code numbers will allow determination of whether ED subjects and/or their referrals use the IWTK website but will not allow research team access to identity-linked test results (Please see data management section below regarding de-identification before data analysis). At the 1-month and 3-month phone follow-up, we will ask participants if they are able to give the referral cards to their partner(s) or friend(s), how many cards they are able to give out, how many cards they are able to give to their partner(s), how many cards they are able to give to their friend(s), and how likely it is that their partner(s) and/or friend(s) will request an HIV self-testing kit from the IWTK website. Finally, we will ask them how we can increase the likelihood of their partner(s) and/or friend(s) accessing the IWTK website and requesting an HIV self-testing kit.

Data management

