IWTK website is an HIPAA compliant, secure website [please see IRB-approved protocol (IRB00063291)]. Drs. [name] and [name], and [name] are the research team members for the current eIRB protocol (IRB00090921) and IRB-approved protocol (IRB00063291). [name] will manage the IWTK dataset according to the IRB-approved protocol (IRB00063291). All study data will be secured electronically on password-protected files in a password protected, encrypted drive on the departmental server with access password restricted to the study investigators and designated staff who have completed appropriate research training and are part of the study team. All data will be kept on Johns Hopkins School of Medicine servers and will not be transmitted or transferred outside of Johns Hopkins. [name] does not have access to IWTK dataset with identifiers. [name] will de-identify the IWTK dataset and provide de-identified data to [name] for data analysis

Access Controls: Only Drs. [name] and [name], [name], and the research coordinators who have completed appropriate research training and on the IRB protocol have the access to the data. The general data access controls are under Johns Hopkins School of Medicine IT and Department of Emergency Medicine. The data files will also be password-protected.

Access Log-in: There will be multi-level log-in control to access the study data. They include JHMI log-in, departmental server access, and data file password log-in.

Data Security: All study data will be secured electronically on password-protected files in a password protected, encrypted drive in the departmental server with access control and multi-level log-in control by Johns Hopkins School of Medicine IT and Departmental IT. All of the data will not be transferred or transmitted out from Johns Hopkins School of Medicine Server. For this research protocol, we will plan to destroy the participant's identifiers at the earliest opportunity – i.e. 3-6 months after the enrollment after we make sure that the participant completes the follow-up survey and receives the incentive that we mail.

- b. Study duration and number of study visits required of research participants.**
The study duration of this pilot study will be 1 year. Each consented participant will have their surveys completed during their ED visit, a phone or text message reminder within one week after the enrollment, and will have one follow up phone call at one-month and three-month time point after enrollment, respectively.

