The primary outcome variables include (1) the uptake of HIV self-testing kit among ED patients who decline conventional ED health professional-based HIV testing and to increase the perceived engagement of HIV testing at a regular basis for those with an increased risk for HIV (the index participants); (2) the relative engagement of HIV testing in one month among the index participants with provision of HIV self-testing kit as compared to those without HIV self-testing kit; (3) number of successful referrals for HIV self-testing kit request from the index participants to their partners or peers of their drug, sex, and social network.

b. Secondary outcome variables.

Participant's attitudes and perceptions on conventional health professional HIV testing in the ED as well as home self-testing. Participant's view on his/her partners and peers' attitudes and perceptions on conventional health professional HIV testing in the ED as well as home self-testing.

c. Statistical plan including sample size justification and interim data analysis.

Descriptive data analysis will be performed at the end of the study.

This is a pilot feasibility and acceptability study. We will plan to enroll a total of 200 ED patients (100 in the self-testing group and 100 in the reference group). For 100 participants in the self-testing group, each of them will refer up to 5 partners/peers to IWTK website to request STI screening kit/HIV self-testing kit. Sample size justification is not required. There will be no interim data analysis.

d. Early stopping rules.

N/A

8. Risks

a. Medical risks, listing all procedures, their major and minor risks and expected frequency.

The HIV self-testing kit is an FDA-approved home testing kit which is available over the counter. There should be no medical risks to the participants other than a potential psychological discomforts related to the survey, and if the patients has a positive test result.

b. Steps taken to minimize the risks.

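### Does a rewarded website report, open only to the kit group, bias the one-month comparison of HIV testing?

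*Combined protocol and SAP*

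**What the plan says.** Section 7a lists as its second primary outcome "the relative engagement of HIV testing in one month among the index participants with provision of HIV self-testing kit as compared to those" without one. It does not define engagement, name a data source or give a rule for patients who are not reached. Section 7c plans descriptive analysis only, with 100 patients per group, no sample size justification and no interim analysis.

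Section 4a describes two ways in which later testing could come to light.

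- **Website, kit group only.** Under Enrollment: "Participants in this group will also receive information regarding how to access the IWTK website to report the completion of HIV self-testing at home". The same item offers a 1 in 10 chance of a $50 "gift card for reporting the test results to the IWTK website". The item on home self-testing repeats the request: "they will be asked to report their test result on to IWTK website using the access information provided in the HIV self-testing kit". The reference group gets something else: "For patients who are in the reference group, a standard pamphlet regarding the importance of HIV testing and HIV testing venues in Baltimore City".
- **Phone, both groups.** Under Patient Follow-up, every consented patient is called at one and at three months and asked about HIV testing since the index visit. At most five attempts are made "until deemed lost to follow up for the particular follow up time point". Section 10 gives the same $10 card per completed call in both groups.

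Under Aim 3, "The confidential code numbers will allow determination of whether ED subjects and/or their referrals use the IWTK website". The same sentence adds that the research team will not get test results linked to identity. Under Data management, a team member "will de-identify the IWTK dataset and provide de-identified data to" a colleague for analysis; no outcome is named there.

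**The concern.** A comparison between groups needs testing to be recorded in the same way in each. Here the kit group has a second, rewarded route and the reference group does not. If a patient counts as tested on either a phone answer or a website report, a kit-group tester who misses the one-month call can still be counted. A reference-group tester who misses it has no such route at that time point.

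The extra route can only add testers to the kit group, so the error would favour the hypothesis in section 1 that the kit increases testing. Analysing by assigned group, or adding a confidence interval, would not remove it. Since section 7 neither includes nor excludes website reports, an analyst could pool them without breaking any written rule.

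**Working it through.** The plan gives no testing rate, phone response rate or website reporting rate, so there is no figure of its own to reproduce beyond 100 + 100 = 200. The rates below are assumptions.

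**Inputs.** r = share reached by phone at one month, equal in both groups; p = share tested among those reached; u = share tested among those not reached; k = share of kit-group tests that are kit tests and so reportable on the website; w = share of unreached kit-group testers with a reportable test who report it. No true effect.

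**Pooled sources, no record counted as not tested.** Kit group = r·p + (1−r)·u·k·w. Reference group = r·p. False difference = (1−r)·u·k·w.

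With p = u = 0.30 and k = 1:

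| r | Reference | Kit, w = 0.25 | Kit, w = 0.75 | False difference | Ratio |
|---|---|---|---|---|---|
| 0.8 | 0.240 | 0.255 | 0.285 | +1.5 to +4.5 points | 1.06 to 1.19 |
| 0.6 | 0.180 | 0.210 | 0.270 | +3.0 to +9.0 points | 1.17 to 1.50 |

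**Pooled sources, only patients with some record.** Kit group = [r·p + (1−r)·u·w] / [r + (1−r)·u·w], with k = 1; reference group = 0.30.

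- r = 0.8: 0.255/0.815 = 0.313 to 0.285/0.845 = 0.337, or +1.3 to +3.7 points.
- r = 0.6: 0.21/0.63 = 0.333 to 0.27/0.69 = 0.391, or +3.3 to +9.1 points.

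**How far the inputs matter (no record counted as not tested).**

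- If unreached patients test half as often (u = 0.15, k = 1): 0.2 × 0.15 × w gives +0.75 to +2.25 points at r = 0.8, and 0.4 × 0.15 × w gives +1.5 to +4.5 at r = 0.6.
- If, in addition, half of the kit-group tests are kit tests (k = 0.5): about +0.4 to +1.1 points at r = 0.8 and +0.75 to +2.25 at r = 0.6.
- The upper values of w suppose that people who missed up to five calls worth a certain $10 then respond to a lottery worth 0.1 × $50 = $5 on average. Nothing in the documents supports a particular value.
- Patients missed at one month are due another call at three months, again about testing since the index visit. If a share c of them is reached then, and their answers are used, the false difference shrinks by the factor 1−c. The documents do not say whether that call would date the test.

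**Scale.** 1.96 × √(2 × 0.3 × 0.7/100) = 0.127, a half-width of 12.7 points.

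**Phone call as the only source.** Website reports then play no part, which is the same as w = 0. Both groups are r·p, so the false difference is 0 and the ratio 1.00 for any p and any equal reach.

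**The case for a change.** The best case for a change is that outcome 2 is a primary outcome and nothing written stops the unfavourable choice. The codes show whether ED subjects used the website, lottery entrants are notified by text, so some operational link exists, and IWTK data do go to analysis. With poor follow-up the tilt need not be small. At 50% reach, 40% tested and w = 0.75, pooling gives 0.35 against 0.20, or +15 points, which exceeds the half-width of 13.6 points at 40%. A descriptive comparison also needs like-for-like measurement, and the remedy would cost only a few sentences.

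Part of this stands. Section 7 does leave the source unnamed, and pooling would tilt the result one way. But the argument needs a step that the documents never take, namely counting website reports towards outcome 2. It also gives too little weight to the shared call. The withholding of identity-linked results and the de-identification before analysis make person-level pooling of results less likely, though they do not exclude it. The phone script and the separate IWTK protocol are cited but not among the documents, and either may settle how testing is recorded.

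**Conclusion.** No change to the plan follows. An instrument common to both groups exists, falls at the time point that outcome 2 specifies, covers HIV testing since the index visit and carries the same payment. Followed as written, the plan contains no rule that produces a wrong comparison. Taking outcome 2 from the one-month call, treating unreached patients alike in the two groups and describing website reports for the kit group alone is what a careful analyst would do without further instruction.

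Under that reading the tilt is zero, assuming equal phone reach. Under pooling it would favour the kit by roughly 0.4 to 9 points in the 60% to 80% reach scenarios above, below the 12.7-point half-width, and it would exceed the noise only with much poorer reach and heavy website reporting. All these sizes rest on assumed rates. Both sources are self-report in an open trial, so a common source equalises capture but does not remove reporting bias. Section 7c plans only description, and no test or decision rule rests on this outcome.

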One approach to narrowing the testing gap is to offer HIV self-testing, which offers an alternative innovative approach outside of the traditional modes of engaging patients, with potential to reach difficult to reach populations. Self-testing at home decreases the stigma and privacy barriers associated with a conventional health professional-based testing model, and may significantly increase HIV testing uptake, thereby potentially decreasing the number of undiagnosed HIV.¹⁰ Many partners and peers of individuals at risk for HIV are also hard-to-reach population.¹¹ Network snowballing recruitment approach has successfully used to identify persons with undiagnosed HIV infection.¹²⁻¹⁶ This approach will significantly improve the participation and involvement of those hard-to-reach high risk populations.

First, we hypothesize that the provision of an HIV self-testing kit to ED patients who decline conventional ED-based HIV testing will be acceptable for these “refusers” and this approach will increase the uptake and engagement of overall HIV testing. Second, we hypothesize that the provision of an HIV self-testing kit to ED patients who are at increased risk for HIV will be acceptable and will increase the engagement of HIV testing at regular basis. We also hypothesize that partners and peers of the testing “refusers” or ED patients with increased risk for HIV will request an HIV self-testing kit for HIV testing if they are referred by their partners or friends.

2. Objectives (include all primary and secondary objectives)

The proposed pilot research has three aims: 1) to determine the feasibility and acceptability of provision of HIV self-testing kit (OraQuick *ADVANCE*® Rapid HIV-1/2 Antibody Test) in order to increase uptake and engagement of HIV testing among ED patients who decline conventional ED health professional-based HIV testing and to increase the engagement of HIV testing at a regular basis for those with an increased risk for HIV (the index participants); 2) to determine the uptake and engagement of HIV testing by provision of HIV self-testing kit; and 3) to determine the feasibility and acceptability of HIV self-testing kit referral among partners or peers of the index participants through drug, sex, or social networks.

3. Background (briefly describe pre-clinical and clinical data, current experience with procedures, drug or device, and any other relevant information to justify the research)

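### Does primary outcome 2 compare patients by whether they took the kit, rather than by randomised group?

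*Combined protocol and SAP*

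**What the plan says.** Section 4a (Enrollment) randomises consented patients to an Index Group or a Reference Group. It describes the first arm thus: "The index group or the HIV self-testing kit group will be provided a free FDA-approved HIV self-testing home kit". The reference arm is not given one. The same paragraph then makes acceptance voluntary: kit-group patients are told of the kit and "they will be asked if they would like to take a free FDA-approved HIV self-testing home kit home". It continues: "If they agree, the research staff will make sure the patients will take the kit home when they are discharged".

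Section 7a lists three primary outcomes. The first includes "the uptake of HIV self-testing kit among ED patients who decline conventional ED health professional-based HIV testing". The second is relative engagement in HIV testing at one month "among the index participants with provision of HIV self-testing kit as compared to those without HIV self-testing kit". Section 7c plans 100 patients in the self-testing group and 100 in the reference group, with descriptive analysis at the end of the study. It names no analysis set.

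The term for the participants is not used uniformly. Section 2, the Aims 1 and 2 statement in Section 4a, and outcome 1 in Section 7a attach it to the enrolled cohorts: "for those with an increased risk for HIV (the index participants". The Aim 3 text in Section 4a uses it close to the kit arm: "the participants (the index participants) in the HIV self-testing kit group in Aim 1 receive the self-testing kit".

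**The concern.** Taking the kit is decided after randomisation, and making uptake an outcome implies that some patients will decline. A kit-arm patient who declines is, in the literal sense, without a kit. Outcome 2 could therefore be read as placing that patient in the comparator, or in neither group. If the participant label meant only the kit arm, outcome 2 would compare takers with decliners inside one arm.

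Patients who decline a free kit, some of whom have just refused an ED test, may be less willing to test by any route. Grouping by receipt would credit that difference in willingness to the kit. Outcome 2 is also the primary outcome that most directly contrasts the two randomised arms, so a wrong grouping there would waste the randomisation.

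**Working it through.** **Step 1: the plan's own figure.** Section 7c gives 100 + 100 = 200, which agrees with the stated total. There is no power or event-rate calculation to reproduce.

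**Step 2: which grouping the text supports.**

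- *Provision.* The study title and the hypotheses in Section 1 use provision for what the study does. Acceptability is the patient's response to it. A patient who is offered a kit and declines still belongs to the provision strategy.
- *Arm descriptions.* Section 4a says one arm is provided the kit and the other does not receive it. Outcome 2 repeats that contrast, with and without.
- *Group sizes.* Section 7c describes groups of 100 and 100. Grouping by receipt would give 90 v 110 or 70 v 130 at 90% or 70% uptake, and the protocol describes no such groups.
- *Participant label.* Outcome 1 attaches it to the enrolled refusers and high-risk patients, and outcome 2 follows in the same sentence. With that meaning, outcome 2 spans both arms. With the narrower meaning, the reference arm would play no part in the comparison of testing.
- *Data.* Section 4a (Patient Follow-up) contacts all consented patients at one month, whether or not they took a kit. Outcome 1 requires kit acceptance to be recorded. The randomised comparison can be made with what is already collected.

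**Step 3: what grouping by receipt would do.** The documents give no uptake or one-month testing rates for this study, so every input here except the 100 per arm is an assumption. Let *u* be uptake, *pT* the testing rate of would-be takers and *pD* that of decliners, the same in both arms (no kit effect).

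- By assigned arm: both arms test at *u·pT* + (1 − *u*)·*pD*, so the difference is 0 at any uptake.
- Kit holders v everyone without a kit: 100*u* patients v 100(2 − *u*). Difference = 2(1 − *u*)(*pT* − *pD*)/(2 − *u*).
- Kit holders v reference arm, decliners dropped: difference = (1 − *u*)(*pT* − *pD*).

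Example with *u* = 0.70, *pT* = 0.50, *pD* = 0.10: 2 × 0.30 × 0.40/1.30 = 0.185 for the first receipt grouping, and 0.30 × 0.40 = 0.120 for the second.

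| Assumed rates, takers v decliners | Uptake | By assigned arm | Holders v all without kit | Holders v reference arm |
|---|---|---|---|---|
| 50% v 10% | 90% | 0 | 7.3 points | 4.0 points |
| 50% v 10% | 70% | 0 | 18.5 points | 12.0 points |
| 30% v 10% | 90% | 0 | 3.6 points | 2.0 points |
| 30% v 10% | 70% | 0 | 9.2 points | 6.0 points |
| 20% v 10% | 90% | 0 | 1.8 points | 1.0 points |
| 20% v 10% | 70% | 0 | 4.6 points | 3.0 points |
| equal rates | any | 0 | 0 | 0 |

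For scale, the 95% half-width for a difference between two arms of 100 is at most 1.96 × √(2 × 0.25/100) = 0.139, or 13.9 points.

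**The case for a change.** The strongest case for a change is that nothing in the plan states the rule. Section 7c uses the names of the randomised groups, but outcome 2 does not. No sentence says where decliners are counted, and the participant label is used in a wider and a narrower sense; Section 10 also leans to the narrower one. A descriptive table still needs defined columns, and a grouping picked after the data are seen could flatter the kit. Selection is plausible, because one cohort consists of patients who have just declined a test. Saying so in a clause would cost nothing.

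Part of this stands: the analysis set is unstated and the label is loose. What does not stand is the step from there to a non-randomised comparison. The reading by receipt needs provision to mean possession, against the protocol's own usage, and group sizes that Section 7c does not describe. The takers-against-decliners reading also needs the label to change meaning within one sentence of Section 7a.

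The larger bias figures lean on their inputs. A 50% testing rate means that half of the would-be takers in the reference arm, holding no kit, test within a month, and no document supports that. Using the 51% in Section 3 as a low value for uptake would be a stretch too: it is a stated preference for testing at home over a clinical setting, not acceptance of a free kit.

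**Conclusion.** No change to the plan is needed. Outcome 2 is loosely worded, but read with the title, Section 4a and Section 7c it compares the arm provided with kits against the reference arm, 100 v 100. Analysed that way, decliners stay in the kit group and the expected difference under no effect is 0 at any uptake. The spurious differences of 1.8 to 18.5 points (uptake 90% to 70%, holders against all without a kit) depend on assumed rates and on a grouping the protocol does not otherwise describe. They vanish if takers and decliners test at the same rate or if everyone takes the kit.

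The gap is one that an analyst fills sensibly: tabulate by assigned arm, report kit uptake beside it, and treat any result by kit receipt as non-randomised. The data for this are already planned. How to count patients not reached at one month is a separate question. The conclusion rests on the natural reading of provision. If the trial were analysed by kit receipt after all, the concern would apply in full to that analysis.

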HIV testing is recommended for all individuals aged 13-65 years.¹ Recent CDC data indicate that > 50% of Americans aged 18-64 years report never having been testing for HIV.^{17,18} They could be those who are unengaged with conventional health professional based testing at the medical care setting such as emergency departments (EDs) where the HIV testing decline rate is up to 50 - 60%.^{8,9} Or, they could be disfranchised hard-to-reach populations who are much less accessible to health care.

HIV seroprevalence in JHH ED patients increased from 5.2% in 1987 to 11% in the early 2000s and decreased to 7.8% in 2007 and 5.6% in 2013 (eIRB protocol NA_00027191, NA_00085477). An ED HIV testing program was implemented in the JHH ED in 2005, where it continues today (eIRB protocol - NA_00044965, *Rapid On-Site HIV Testing in the Emergency Department (ED)*). Currently, up to 50 to 60% of JHH ED patients decline to be tested when non-targeted offering of HIV testing is made available to all patients (IRB00051816).

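### Primary outcome 2 is a randomised comparison, but section 7c makes no use of cohort or prior HIV testing, which could sharpen it modestly at almost no cost

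*Combined protocol and SAP*

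**What the plan says.** Section 7a (Primary outcome variable) lists as its second primary outcome "the relative engagement of HIV testing in one month among the index participants with provision of HIV self-testing kit", set against participants without the kit. Section 4a (Enrollment) randomises consented patients to the kit group or the reference group and states no stratification factor. Section 7c plans 200 patients, 100 in each group.

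The analysis plan in section 7c is one sentence: "Descriptive data analysis will be performed at the end of the study". It names no effect measure, interval, model or covariate. The same section says "This is a pilot feasibility and acceptability study" and "Sample size justification is not required".

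Two kinds of baseline information are available:

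- **Cohort.** Sections 4a and 5 define two groups of patients: refusers, who declined the triage offer of a test, and high-risk patients, who accepted the standard-of-care test. Every participant's cohort is fixed by eligibility.
- **Testing history.** Under Enrollment in section 4a, both groups complete "a short survey regarding their socio-demographic information as well as their experience, attitudes, and perceptions regarding HIV testing". The questionnaire itself is an attachment and is not in the document.

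Neither is given a role in the analysis.

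**The concern.** In a trial of this size the groups can differ by chance in how many patients have tested before, or in how many refused the triage test. If such a factor predicts testing during the next month, part of the observed kit-versus-no-kit difference reflects that imbalance. A descriptive comparison of two proportions leaves it there and carries slightly more variance than it needs to.

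The plan also gives no rule for the case where the baseline table shows an imbalance. A decision to adjust taken at that stage would be made with the results in view. Naming the baseline factors beforehand avoids this.

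**Working it through.** **The plan's own figure.** The total of 200 cannot be reproduced. Section 7c gives no error rate, power, effect size or outcome rates.

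**Inputs**

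- n = 100 per group (section 7c), at first with no loss to follow-up.
- q = 50% previously tested. This is an assumption. Its only guide is the national figure in section 3 that more than "50% of Americans aged 18-64 years report never having been testing for HIV". The trial's own value is not given.
- b = 10, 20 or 30 points: how much more often prior testers test within one month than never-testers. Assumed; the documents give no value.
- One-month testing of 20% v 40%, or 30% v 50%. Assumed.

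**Step 1: size of chance imbalance in prior testing.** SD = √(2q(1−q)/n) = √(2 × 0.25/100) = 7.1 points. The 95% range is ±1.96 × 7.07 = ±13.9 points. The chance of a gap of 10 points or more in either direction is 2 × (1 − Φ(0.10/0.0707)) = 16%. With q = 30% the SD is 6.5 points and the chance is 12%.

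**Step 2: how much of it reaches the kit effect.** Shift = imbalance × b.

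| b (points) | Shift at a 10-point gap | SD of the shift | 95% range of the shift |
|---|---|---|---|
| 10 | 1.0 | 0.7 | ±1.4 |
| 20 | 2.0 | 1.4 | ±2.8 |
| 30 | 3.0 | 2.1 | ±4.2 |

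**Step 3: precision gained.** Unadjusted variance is V = [p0(1−p0) + p1(1−p1)]/n. Adjusted variance is V − 2b²q(1−q)/n. At 20% v 40%, V = (0.16 + 0.24)/100 = 0.0040. At 30% v 50%, V = (0.21 + 0.25)/100 = 0.0046.

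| Rates | b | SE, unadjusted → adjusted (points) | SE reduction | 95% half-width (points) |
|---|---|---|---|---|
| 20% v 40% | 10 | 6.32 → 6.28 | 0.6% | 12.4 → 12.3 |
| 20% v 40% | 20 | 6.32 → 6.16 | 2.5% | 12.4 → 12.1 |
| 20% v 40% | 30 | 6.32 → 5.96 | 5.8% | 12.4 → 11.7 |
| 30% v 50% | 10 | 6.78 → 6.75 | 0.5% | 13.3 → 13.2 |
| 30% v 50% | 20 | 6.78 → 6.63 | 2.2% | 13.3 → 13.0 |
| 30% v 50% | 30 | 6.78 → 6.44 | 5.0% | 13.3 → 12.6 |

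The outer limits come from R² = 0.25b²/(p(1−p)) for an overall risk p of 20% to 40%. With b = 10 and p = 40%, R² = 0.0025/0.24 = 0.010, an SE cut of 0.5%. With b = 30 and p = 20%, R² = 0.0225/0.16 = 0.141, an SE cut of 7.3%. In patients this is 1/(1−R²) − 1, or about 1% to 16% more.

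**Step 4: check by simulation.** 40,000 trials were simulated with 100 per group, 30% v 50%, q = 50% and b = 20. The unadjusted difference averaged 20.0 points for a true 20, and its 95% interval covered the truth 94.5% of the time. Among trials with a kit-group excess of at least 10 points in prior testing, the unadjusted difference averaged 22.6 points and the adjusted one 20.1.

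**Step 5: loss to follow-up.** No rate is given. With 70 per group at one month (an assumed 30% loss) and q = 50%, the SD of the shift becomes 0.8, 1.7 or 2.5 points for b = 10, 20 or 30. The unadjusted half-width becomes 14.8 points (20% v 40%) or 15.9 points (30% v 50%).

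The Step 1 and Step 2 formulas apply equally to cohort. The documents give neither the cohort mix nor its link with later testing, so no figure is put on it.

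**The case against.** The strongest case against is that this is a pilot with a declared descriptive purpose. Randomisation makes the unadjusted contrast unbiased on average, and an ordinary 95% interval already allows for chance imbalance, as the 94.5% coverage shows. The gain in precision is small, and the larger deficiency is that no estimate with an interval is planned at all. All of this stands. It makes the point an inexpensive improvement rather than a flaw that invalidates the comparison. It does not remove the point, because outcome 2 is listed as primary and section 7c does not supply the interval on which this defence relies.

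Three further objections hold in part.

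- The text does not exclude adjustment. That it will be unadjusted is inferred from a single sentence naming no covariate.
- The questionnaire is not shown, so a usable prior-test item is unconfirmed. Cohort, in contrast, is known for everyone.
- The national figure may not describe this emergency department, which has run a testing programme since 2005. A value of 50% also gives the largest imbalance.

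A reader might go further and infer that an imbalance passes in full into the kit effect, or that prior testing is the strongest predictor collected. The documents support neither. The imbalance is first multiplied by a predictor strength that they do not state, and cohort may matter at least as much.

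A reader might also expect larger gains for attitude and perception answers, since enrolment and follow-up both cover them. That would require scored, repeated items with a known correlation, recorded before the patient knew the assignment. None of this is documented, and section 4a describes randomisation before it describes the survey.

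**Conclusion.** The point holds as a modest improvement that costs almost nothing. Section 7c leaves a primary randomised contrast to description and does not use baseline facts that the trial holds or can readily obtain. The unadjusted comparison is valid over randomisation. The benefit of adjusting for prior testing is the small SE reduction and the removal of most of the shift in the minority of trials with a visible imbalance. Even at the strong end of the assumed range, the SD of that shift is about 2 points, well inside the interval's half-width.

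These sizes rest on assumed prevalence, predictor strength and outcome rates. That section 7c names no baseline factor does not depend on them.

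**What to change.** In section 7c, add for outcome 2:

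*The proportion tested for HIV by one month, not counting the standard-of-care test at the index visit, will be compared between the randomised groups as a risk difference and a risk ratio, each with a 95% confidence interval, standardised over cohort (refuser, high-risk acceptor) and over HIV testing history before the index visit from the enrolment survey. The unadjusted estimates will be shown beside them.*

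The risk ratio keeps the relative measure that section 7a names, and the risk difference gives the absolute effect. The index-visit test is left out because the high-risk cohort accepts it in both groups, so it says nothing about the kit.

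If the survey has no prior-test item, either adjust for cohort alone or add that one item. It should be a factual history item, which the assignment cannot change, and not an attitude item.

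The cost is two sentences in section 7c, a few lines of analysis code and at most one survey item. No further patients, visits or staff are needed.
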